5.11 Pharmacokinetic Concentrations

Steady state concentrations of A-1684909 in plasma will be assayed using validated liquid chromatography-tandem mass spectrometry methods by AbbVie. Additional active or inactive metabolites of interest in plasma may also be assayed using validated or non-validated methods. For summaries, A-1684909 and metabolite levels that are below the limit of quantitation will be reported as zero. For analyses, A-1684909 and metabolite levels will be log-transformed and levels that are below the limit of quantitation will be imputed at the limit of quantitation divided by two.

Repeated measures analysis (linear mixed effects) of the log-transformed dose-normalized A-1684909 plasma trough concentrations will be performed to evaluate dose proportionality. Dose, visit (Week 4, Week 8, Week 16, and Week 24), and their interaction will be fixed effects. The effect of dose will be estimated from a one degree of freedom contrast between the ABBV-CLS-7262 120 mg and 240 mg dose groups averaged over the four visits. The hypothesis will be that there is no significant effect of dose on the dose-normalized concentrations across all visits.

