2.6 Treatment Allocation

Approximately 300 participants assigned to RGF who are determined eligible will be randomly allocated to one of two ABBV-CLS-7262 dosages or placebo. Approximately 165 will be randomized to ABBV-CLS-7262 administered QD at a dosage of 120 mg, approximately 60 participants will be randomized to ABBV-CLS-7262 administered QD at a dosage of 240 mg, and approximately 75 participants will be randomized to placebo. Treatment assignments are based on a pre-specified permuted-block randomization schedule stratified for all combinations of use vs. non-use of riluzole, edaravone, and sodium phenylbutyrate/taurursodiol (Relyvrio® or Albrioza®) at the time of screening for the Master Protocol. The first 240 participants will be assigned in a 2:1:1 allocation ratio to 120 mg ABBV-CLS-7262, 240 mg ABBV-CLS-7262, or placebo. The final approximately 60 participants will be assigned in a 3:1 allocation ratio to 120 mg ABBV-CLS-7262 or placebo by interpreting any assignments to 240 mg ABBV-CLS-7262 as an assignment to 120 mg ABBV-CLS-7262.

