5.12 Participant Compliance

For objective analysis, participants who are non-compliant with study drug administration will be identified by plasma concentrations of A-1684909 that are less than 10 ng/mL at any visit during the placebo-controlled period of the study.

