6.1 Analysis Sets

The following analysis sets will be used for testing efficacy, pharmacokinetics, and safety endpoints:

- Efficacy Full Analysis Set (FAS): Participants who were randomized within RGF plus
 placebo participants from Regimens A, B, C, D, E, G, classified according to their
 randomized treatment assignment. Observations made after premature permanent
 discontinuation of study drug are included in this sample, should such participants remain on
 study. Observations completed after regimen data lock will be excluded. Participants
 determined to not meet ALS diagnostic criteria are excluded.
- Efficacy Concurrent-controls (ECC) Set: The subset of participants in the FAS analysis set
 who were randomized within RGF or randomized to placebo within RGG at or prior to the
 date when the last RGF participant was randomized, exclusive of RGG participants who were
 also randomized within RGF. This is the primary analysis set for primary and secondary
 analyses.
- Efficacy Regimen-only (ERO) Set: The subset of participants in the FAS analysis set who
 were randomized within RGF.
- Efficacy Common Mode of Administration (ECM) Set: The subset of participants in the FAS
 analysis set from Regimens B, C, D, F, G, and any other regimens in which study drug is
 administered orally.
- Efficacy Per-protocol (EPP) Set: The subset of participants in the ECC analysis set who initiated study treatment and who meet other requirements for protocol compliance as specified in the R-SAP, including compliance taking study drug (defined in Section 5.12), classified according to the treatment they actually received. If a participant's data are truncated for inclusion in the EPP analysis set due to a time-dependent event (e.g., non-adherence to protocol-specified dosing, initiation of a prohibited medication, initiation of a medication approved for treatment of ALS), clinical events observed after the censoring event will be excluded from the EPP analysis set. Data from placebo participants shared from other regimens will not be truncated due to non-adherence to protocol-specified dosing. Final specification of participants included vs. excluded from the EPP analysis set will be defined prior to data lock.
- Pharmacokinetic Analysis (PKA) Set: Participants who received at least one dose of active ABBV-CLS-7262 within RGF and from whom at least one PK sample was collected.

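### Dose proportionality in SAP 5.11 rests on a non-significant difference, and BLQ troughs set to LOQ/2 can distort the 240/120 contrast

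*SAP*

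**What the plan says.** SAP 5.11 gives the purpose of the model: "Repeated measures analysis (linear mixed effects) of the log-transformed dose-normalized A-1684909 plasma trough concentrations will be performed to evaluate dose proportionality". Dose, visit (Weeks 4, 8, 16 and 24) and their interaction are fixed effects. The dose effect is to be estimated by a single contrast of the two active groups, taken as a mean across those visits. The hypothesis reads: "The hypothesis will be that there is no significant effect of dose on the dose-normalized concentrations across all visits". No equivalence bounds, confidence-interval criterion, alpha or power is stated for this analysis.

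For analyses, as opposed to summaries, "levels that are below the limit of quantitation will be imputed at the limit of quantitation divided by two". The value of the LOQ is not given. Nor does the section say whether the imputation comes before or after division by dose.

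The PK analysis set in SAP 6.1 is defined as: "Participants who received at least one dose of active ABBV-CLS-7262 within RGF and from whom at least one PK sample was collected". SAP 5.12 flags non-compliant participants by "plasma concentrations of A-1684909 that are less than 10 ng/mL at any visit during the placebo-controlled period". That flag feeds the per-protocol efficacy set (SAP 6.1) and the compliance summary (SAP 6.7.2), not the PK set. SAP 4.5 and protocol 2.3 make dose contrasts the main interest among PK endpoints, while treating 240 mg comparisons in general as exploratory.

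**The concern.** There are two separate problems.

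- **The criterion.** Proportionality is the null hypothesis of a difference test. Failing to reject it can mean that the doses are proportional or that the data are too noisy. The stated criterion cannot tell these apart.
- **The BLQ rule.** The PK endpoint is a steady-state concentration. Protocol 5.5 projects troughs above 40 ng/mL in more than 95% of participants on 120 mg, so a BLQ trough in a treated participant most likely reflects missed or stopped dosing. If the same LOQ/2 is entered in both arms and then divided by dose, the 240 mg value is half the 120 mg value whatever the drug does.

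Off-drug samples have a documented way in. Protocol 6.10 lets participants who stop study drug remain under follow-up, and protocol 8.1 draws a PK sample at every clinic visit of the placebo-controlled period. An Early Termination Visit repeats the Week 24 assessments, including PK, and may fall more than 28 days after the last dose. SAP 3.6 then assigns such an observation to the nearest missing scheduled visit.

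At stake is the statement on dose proportionality and its use in reading the exploratory exposure-response data.

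**Working it through.** The plan states no power or precision for this analysis, so there is no figure of its own to reproduce.

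**Inputs from the documents**
- Arm sizes: "Approximately 165 will be randomized to ABBV-CLS-7262 administered QD at a dosage of 120 mg" and "approximately 60 participants will be randomized to ABBV-CLS-7262 administered QD at a dosage of 240 mg" (SAP 2.6). The allocation agrees: 240 × 2/4 + 60 × 3/4 = 165 and 240 × 1/4 = 60.
- Attrition (SAP Appendix 1, section 3.1): 2% monthly dropout and 5% mortality over 24 weeks. 0.98^(168/30.4375) × 0.95 = 0.850, leaving about 140 and 51 at Week 24.
- Variability: no plasma trough CV is given. The only spread given for A-1684909 is in CSF (protocol 1.1): 0.47/2.4 = 20% and 3.0/6.3 = 48%.

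**Assumed:** two-sided alpha 0.05; log SD = √ln(1 + CV²), with CV varied from 30% to 100%.

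**1. What the difference test can see, with no BLQ values.** SE = SD × √(1/165 + 1/60) = 0.151 × SD. At CV 48%, SD = 0.455 and SE = 0.069. The ratio detectable with 80% power is exp(2.80 × 0.069) = 1.21. Equivalence power uses the 90% CI, assumed bounds 0.80–1.25 and a true ratio of 1.

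| CV | Power for a true ratio of 1.25 | Equivalence power |
|---|---|---|
| 30% | >99% | >99% |
| 48% | 90% | 89% |
| 60% | 76% | 69% |
| 80% | 56% | 35% |
| 100% | 43% | 11% |

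Power for a 25% departure is at least 80% up to a CV of about 57% (about 52% with 140 and 51).

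**2. BLQ bias with equal shares.** ln[(LOQ/2)/240] − ln[(LOQ/2)/120] = −ln 2, whatever the LOQ. With BLQ share f in both arms and true proportionality, the ratio is 2^(−f): 0.986 at 2%, 0.966 at 5%, 0.933 at 10%, 0.871 at 20%.

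**3. BLQ bias with unequal shares.** Assume a median trough of 80 ng/mL at 120 mg and 160 ng/mL at 240 mg (exact proportionality), with 5% BLQ on 120 mg and 10% on 240 mg.
- LOQ 5: 0.10 × ln(2.5/160) − 0.05 × ln(2.5/80) = −0.416 + 0.173 = −0.243, a ratio of 0.78.
- LOQ 1: 0.10 × ln(0.5/160) − 0.05 × ln(0.5/80) = −0.577 + 0.254 = −0.323, a ratio of 0.72.

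**4. Simulation.** There were 4,000 trials per setting with four visits. Participant means served as a complete-data approximation to the mixed model. Between-subject CV was 48%, within-subject CV 30%, median trough 80 ng/mL and LOQ 1 or 5 ng/mL, all assumed.
- Equal BLQ shares, true ratio 1: false rejection is 7–8% at 5% BLQ, 7–11% at 10% and 8–21% at 20%.
- True ratio 1.25: power falls from about 87% to 37–48% with 5% BLQ scattered over visits, and to 21–29% if the same participants are BLQ throughout.
- Unequal shares as in step 3, true ratio 1: false rejection is 36–73%.
- Equivalence power with 5% BLQ scattered in both arms: it falls from about 85% to 27% (LOQ 1) or 51% (LOQ 5).

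The bias can also hide a real rise. A true ratio of 1.25 with 20% BLQ in both arms is estimated near exp(0.8 × ln 1.25 − 0.2 × ln 2) = 1.04.

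**The case against.** The strongest reply is that SAP 5.11 plans to estimate the dose effect. On the log scale its contrast already is the log of the dose-normalized geometric mean ratio, and only an interval and a way of reading it are missing. That is correct, and it makes the repair cheap.

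A reader might infer three stronger things that the documents do not support.
- **That p > 0.05 will be reported as proportional.** The SAP does not say so. It frames the hypothesis that way and offers no other criterion.
- **That the test is underpowered.** Step 1 does not show this. If BLQ values are rare, the planned arms detect a 25% departure with at least 80% power up to a CV of about 57%.
- **That missed doses generally mimic non-proportionality.** The LOQ/2 artefact arises only for samples that are BLQ. With equal shares it is 3% at 5% BLQ and 7% at 10%, and false rejection hardly moves.

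The order of imputation and dose-normalizing is likewise inferred. If one constant were substituted after normalizing, the two-fold gap would vanish, though the added variance would remain.

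It is also fair that SAP 6.7.2 already summarizes compliance in the two active groups and that protocol 8.1 tabulates concentrations by visit and dose. Neither changes which samples enter the model. Finally, this analysis lies outside the fixed-sequence efficacy testing, which bears on priority rather than on whether the criterion is sound.

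**Conclusion.** The point holds in limited form. A hypothesis of no significant dose effect, with no margin or interval, cannot support a conclusion of proportionality. On the natural reading of the BLQ rule, each such sample builds in a factor of two between the doses, and nothing in the PK set definition removes samples taken off drug.

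The direct bias is small when BLQ shares are equal. The larger risks are lost precision and, if BLQ shares differ by arm, a false departure: a ratio of 0.72–0.78 under the assumed 5% versus 10%. The documents do not show that shares will differ. These sizes depend on assumed plasma CV, trough level, LOQ and BLQ rates. The −ln 2 gap does not depend on them, only on the order of the two steps.

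Primary and secondary efficacy conclusions are unaffected, and the priority is low.

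**What to change.** In SAP 5.11:
- Report the 240/120 dose-normalized geometric mean ratio with a 90% CI from the same mixed model, and judge proportionality from that interval rather than from non-significance. If a yes/no conclusion is wanted, set the bounds before data lock.
- Restrict this analysis to steady-state evaluable troughs, defined by recorded dosing before the sample.
- Exclude BLQ and off-drug samples, or treat BLQ values as censored. Report their counts by arm, and keep the LOQ/2 analysis as a sensitivity analysis with the order of imputation and normalizing stated.

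The 10 ng/mL threshold in SAP 5.12 should not serve as the sample filter. It classifies participants, not samples, and it is not dose-neutral: 10/120 = 0.083 ng/mL/mg against 10/240 = 0.042 ng/mL/mg. Under proportionality it would remove more low values from the 120 mg arm and push the ratio below 1.

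The cost is SAP wording on the same model and data. Slightly fewer samples will be used, and the interval may be inconclusive if variability is high. With assumed bounds of 0.80–1.25, equivalence power is 89% at CV 48% but 35% at CV 80%. With assumed wider bounds of 0.70–1.43, it is 92% at CV 80%.

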5.12 Participant Compliance

For objective analysis, participants who are non-compliant with study drug administration will be identified by plasma concentrations of A-1684909 that are less than 10 ng/mL at any visit during the placebo-controlled period of the study.

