6.7.2 Study Drug Compliance and Tolerance

Summaries of study drug exposure and tolerance are the same as described in the M-SAP. The proportion of participants who are compliant with study drug as defined in Section 5.12 will be summarized for participants in the ABBV-CLS-7262 120 mg and 240 mg treatment groups. Drug accountability discrepancies will be listed according to Appendix 2.

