In accordance with the SAP for the clinical trial, AEs will be coded using preferred terms from the Medical Dictionary for Regulatory Activities (MedDRA) version 24.0 or higher. Treatment-emergent adverse events (TEAEs) will be defined as any event that begins or worsens in severity after the first dose of study drug and for up to 30 days after the last dose of study drug. Abuse-related AEs will be defined as any TEAEs with preferred terms corresponding to the list in Appendix B.

The number and percentage of subjects having abuse-related AEs will be tabulated by primary System Organ Class (SOC) and MedDRA preferred term with further breakdowns by severity rating and relationship to study drug (as evaluated by the Investigator). Severity rating will be assigned according to the Common Terminology Criteria for Adverse Events (CTCAE) version 4.03 or higher, or as otherwise defined in the SAP for the clinical trial. Subjects reporting more than one abuse-related AE for a given MedDRA preferred term will be counted only once for that term using the most severe incident and the incident with the maximum relationship to study drug. Subjects reporting more than one type of abuse-related AE within a SOC will be counted only once for that SOC.

Listing of Drug Accountability Discrepancies

Drug accountability discrepancies may identify participants who are overusing or abusing study drug.

Drug accountability discrepancies (i.e., instances of participants failing to return unused study drug sachets) are identified in outpatient studies through an eCRF.

The expected return amount of the unused drug is calculated for each participant by:

Expected Return Amount =

Dispensed Amount (#sachets) – Dose
$$\left(\frac{\#sachets}{day}\right) \times$$
 Days Supply (#days)

For outpatient studies only (see Appendix C), a listing will be generated for drug accountability discrepancies where the number of unused sachets that are returned is less than the expected return amount.

Signatures

[figure not shown]

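### The per-protocol drug-compliance test is a plasma drug level, so it can screen the active arms for missed doses but none of the controls

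*SAP*

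**What the plan says.** The EPP set is drawn from the Efficacy Concurrent-controls (ECC) set: Regimen F (RGF) participants plus concurrent Regimen G (RGG) placebo. SAP 6.1 requires protocol compliance, "including compliance taking study drug (defined in Section 5.12), classified according to the treatment they actually received".

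SAP 5.12 has a single test. Non-compliant participants are "identified by plasma concentrations of A-1684909 that are less than 10 ng/mL at any visit" in the placebo-controlled period. It names no arm. Protocol (RSA) 5.7 carries the same rule.

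SAP 6.1 also lets data be truncated at time-dependent events, with these examples: "non-adherence to protocol-specified dosing, initiation of a prohibited medication, initiation of a medication approved for treatment of ALS". It then makes one exception: "Data from placebo participants shared from other regimens will not be truncated due to non-adherence to protocol-specified dosing". It leaves membership open for now: "Final specification of participants included vs. excluded from the EPP analysis set will be defined prior to data lock".

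Two further passages bear on intent. SAP 6.7.2 says the proportion "compliant with study drug as defined in Section 5.12 will be summarized for participants in the ABBV-CLS-7262 120 mg and 240 mg treatment groups", so placebo is not summarized on this measure. The same section adds: "Drug accountability discrepancies will be listed according to Appendix 2". That appendix is the abuse-monitoring plan, and it lists cases "where the number of unused sachets that are returned is less than the expected return amount".

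**The concern.** A per-protocol comparison is informative only if the filter that makes it works alike in the arms being compared. Matching placebo has no active ingredient (RSA 5.3), so a plasma A-1684909 level cannot tell an adherent placebo participant from a non-adherent one. If the rule acts only on active arms, EPP compares 120 mg participants selected after randomization for adequate drug levels with controls who were never selected on adherence.

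At stake is how the EPP results can be read. The set is used for ALSFRS-R total score, upper-limb strength and SVC (SAP 6.5.2 and 6.5.3), for death or death equivalent and death alone (6.5.4), and for the combined function and survival ranking (6.5.5).

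**Working it through.** **Who is in the comparison.** From the allocation rule in SAP 2.6 (first 240 at 2:1:1, final 60 at 3:1) and the RGG planning figure in SAP Appendix 1, section 3.1:

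- 120 mg: 240 × 2/4 + 60 × 3/4 = 120 + 45 = 165
- 240 mg: 240 × 1/4 = 60
- RGF placebo: 240 × 1/4 + 60 × 1/4 = 60 + 15 = 75
- Controls: 75 RGF + 60 RGG = 135

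This reproduces the plan's 165 against 135.

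**Reading 1: the rule as written, no arm restriction.** Every RGF placebo participant has a level below 10 ng/mL and is non-compliant. Controls fall from 135 to 135 − 75 = 60, a loss of 75/135 = 56%, and all who remain come from RGG.

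**Reading 2: active arms only.** The rule can act on 165 participants in the 120 mg comparison, and on 60 more in the exploratory 240 mg comparison. It can act on 0 of 135 controls:

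- 75/135 = 56% (RGF placebo): SAP 6.1 permits truncation for dosing non-adherence, but the R-SAP gives no measure of it.
- 60/135 = 44% (RGG placebo): expressly exempt from that truncation.

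**Do the existing sachet counts fill the gap?** Two cover placebo; neither is tied to EPP.

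- RSA 5.7 has an 80–120% band, but its stated consequence is a discussion with the Medical Monitor.
- SAP Appendix 2 computes expected return = dispensed − (sachets per day × days). All RGF arms take two sachets a day (RSA 5.2), so someone who misses m full days should return 2m more than expected. The listing catches only returns below expectation, that is possible overuse. A participant who skips doses is not listed.

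**What can still act on RGF placebo.** Prohibited medication and newly started ALS medication are named in SAP 6.1 and do not depend on a drug level. Permanent discontinuation can be known in every arm: the Full Analysis Set definition relies on it, and RSA 5.7 provides a Study Treatment Exposure Log for such decisions. What is left uncovered is missed doses and partial adherence while nominally on treatment.

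**Removal or truncation.** SAP 5.12 says only how non-compliant people are identified. SAP 6.1 lists dosing non-adherence among the truncating events, so truncation is the better-supported reading, but the starting visit is not stated. The difference can be large. ALSFRS-R has six scheduled post-baseline visits (Weeks 4, 8, 12, 16, 20 and 24). For one low level at Week 24 only, removal would discard all six and truncation at most one.

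**The case against.** The strongest case on the other side has four parts.

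- **EPP is unfinished.** Membership is to be fixed before data lock, and the list of compliance requirements is open-ended. That leaves room for a repair, but it supplies no arm-neutral measure, and the one measure stated is arm-dependent.
- **The Master SAP may help.** Exposure and tolerance summaries follow it, and it was not among the documents reviewed, so a general adherence rule there cannot be ruled out. Against this, SAP 6.1 points to requirements in the R-SAP and names 5.12, and SAP section 1 gives the R-SAP authority over the Master SAP. This remains the main uncertainty.
- **Plasma levels were chosen for objectivity.** That stands. RSA 5.5 projects troughs above 40 ng/mL in more than 95% of participants on 120 mg, so a 10 ng/mL cut, one quarter of that, is a reasonable non-adherence marker in the active arms. It is a reason to keep the rule there; it does not supply a measure for placebo.
- **Discontinuation is visible in all arms.** This also stands, and it confines the point to missed doses and partial adherence.

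Two stronger readings are tempting. A reader might infer that the plan would empty the RGF placebo arm out of EPP. SAP 6.7.2, and an exemption limited to placebo from other regimens, show this is not the likely intent. A reader might also infer that the EPP result will favour the drug. That needs a non-compliance rate and a link between non-adherence and progression, and the documents give neither.

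**Conclusion.** The point holds as a minor one. As written, the EPP drug-compliance criterion either fails all of about 75 RGF placebo participants or, on the likelier reading, screens up to 165 participants on 120 mg and none of 135 controls for missed doses. That asymmetry follows from the text and needs no assumption about behaviour. The counts are planning figures; the actual number of RGG controls will depend on enrolment.

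No direction or size of bias is claimed. A reader might infer a threat to the trial's main conclusion, but the primary analysis and the hierarchical secondary tests use the ECC set, no success criterion depends on EPP, and the Full Analysis, regimen-only and common-mode sensitivity sets do not use this filter.

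**What to change.** Before unblinding, amend the SAP as follows:

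1. In 5.12, state that the 10 ng/mL rule applies to the active arms only, and keep it for the 6.7.2 summary.
2. In 6.1, define EPP dosing adherence by one sachet-accountability rule, two-sided so that missed doses count, applied identically to 120 mg, 240 mg and RGF placebo. The 80–120% band in RSA 5.7 could serve, purely to define the analysis set. RSA 5.7 does not say over what period the percentage is taken, so the SAP should. Report the EPP version that also applies the plasma rule as supplementary, labelled as filtering the active arms only.
3. Confirm that failing the criterion truncates later data, in line with 6.1, and say from which visit.

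The cost is wording and some extra programming. No new data are needed: unused sachets are already inventoried at clinic visits, and two sachets a day in every arm means one count rule fits all.

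There are two drawbacks. Sachet counts are less objective than plasma levels, and RGG controls remain unscreened for dosing. Reporting EPP without RGG controls is optional. With 75 rather than 135 controls, the standard error grows by a factor of √[(1/165 + 1/75)/(1/165 + 1/135)] = √1.44 = 1.20, assuming equal variances and no exclusions. The regimen-only set already gives an RGF-only comparison without the per-protocol filter.
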